 - (b) Hearing thresholds in the contralateral ear of ≤ 25 dB HL
 - (2) Between 3 years, 6 mos and 6 years, 6 mos of age at implantation.
 - (3) Anatomically normal cochlear nerve
 - (4) Cochlear anatomy that is amenable to cochlear implantation as evaluated by imaging (modality at the physician's discretion) including:
 - (a) Normal cochlear anatomy or

- (b) Incomplete Partition Type II (IP2) with or without Enlarged Vestibular Aqueduct (EVA) or
- (c) EVA with normal partitioning
- (5) No evidence of progressive hearing loss.
- (6) Willing to undergo 4 week hearing aid trial as warranted based on achieving desired audibility when fitted via real ear DSL method. See Reference Appendix B.
- (7) Aided word recognition in the ear to be implanted of 30% or less as measured with CNC words (50-word list)
 - (a) When listening with an appropriately fit hearing aid and masking applied to the contralateral ear (Turner, 2004).
 - (b) Aided testing will be conducted in a sound-proof booth with the participant seated 1 meter from the sound source, facing 0° azimuth. Recorded materials will be presented at 60 dB SPL.
 - (c) The hearing aid output will be measured using DSL targets.
- (8) Realistic parental expectations: *a verbal acknowledgement of the potential benefits and risks, and postoperative variation in performance. For instance, cochlear implantation will not restore normal hearing.*
- (9) Willing to obtain recommended meningitis vaccinations per CDC recommendations.
- (9) Development and cognition within the normal range as measured by the Leiter-R test of nonverbal intelligence and cognitive abilities.
- (10) Parental commitment to study parameters including being able and willing to participate in evaluation schedule, involvement in prescribed therapy, and travel to investigational site and study-related activities.

ii) Exclusion Criteria

- (1) English is not primary language of the home
 - (a) Speech perception materials are presented in English
 - (b) Parental questionnaires are administered in English
- (2) Conductive hearing loss in either ear
- (3) Compromised auditory nerve
- (4) Ossification of the cochlea
- (5) Inability to participate in follow-up procedures (i.e., unwillingness, geographic location)
- (6) History of condition that contraindicates middle or inner ear surgery or anesthesia (i.e. otitis media refractory to treatment)
- (7) Case of sudden sensorineural hearing loss that has not been first evaluated by a physician

iii) Enrollment

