Appendix A graphically depicts the timeline and associated measures

i) **Candidacy Evaluation.** This interval may overlap with the Preoperative Evaluation interval.

- (1) Audiologic Evaluation
 - (a) Unaided air- and bone-conduction thresholds in both ears
 - (i) Air-conduction assessed with inserts
 - (b) Unaided word recognition in both ears
 - (i) Measured with recorded CNC words (50-word list)
 - (ii) Masking provided when appropriate (Turner, 2004)
 - (c) Tympanometry in both ears
 - (d) Aided word recognition in the affected ear
 - (i) Measured with recorded CNC words (50-word list)
 - (ii) Masking applied to the contralateral ear
 - (e) Completion of all questionnaires
 - (f) Determine if potential participant meets candidacy criteria
- (2) Speech-language and psycho-education evaluation
 - (a) Oral Written Language Scale (OWLS-II)
 - (b) Goldman Fristoe Test of Articulation
 - (c) Leiter-R
- (3) Medical Evaluation
 - (a) Determine if potential participant is healthy enough to undergo cochlear implantation
 - (b) Associated imaging studies
 - (c) Discussion of alternative treatment options
 - (d) Determine if potential participant meets candidacy criteria
- (4) Informed Consent
 - (a) Review and discussion of consent form
 - (b) Provide time for participant and/or parents to review consent form and ask questions
 - (c) Provide participant and/or parents with a signed copy of the completed consent form

The Preoperative Evaluation will be completed within 6 months of the surgery date.

- (1) Audiologic Evaluation
 - (a) Obtain a case history, including but not limited to:
 - (i) Onset of hearing loss
 - (ii) Stability or progression of sensorineural hearing loss
 - (iii) Suspected etiology of hearing loss

- (b) Unaided air- and bone-conduction thresholds in both ears assessed with insert phones
- (c) Unaided word recognition with CNC words in both ears
 - (i) Measured with recorded CNC words (50-word list)
 - (ii) Masking provided when appropriate (Turner, 2004)
- (d) Tympanometry in both ears
- (2) Speech-language and psycho-education evaluation
- (3) Parental Questionnaires – will serve as anchor point for future questionnaires
- (4) Counseling of parents on cochlear implant external technology, realistic expectations, study test battery, and postoperative timeline
- (5) Medical Evaluation
 - (a) Participants will undergo a medical assessment and review of medical history
 - (b) Associated imaging studies

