- (d) Assessment of hearing in contralateral ear
- (e) Mapping of the external speech processor

(7) Nine-Months Post-Initial Activation

- (a) Localization assessment
- (b) Parental questionnaires - anchored to prior questionnaires
- (c) Speech perception with the cochlear implant via direct input to processor
- (d) Mapping of the external speech processor

(8) Twelve-Months Post-Initial Activation

- (a) Hearing in noise assessment
- (b) Parental questionnaires - anchored to prior questionnaires
- (c) Speech perception with the cochlear implant via direct input to processor

- (d) Mapping of the external speech processor
- (e) Assessment of hearing in contralateral ear
- (f) Speech-Language evaluation

(9) Eighteen Months Post-Initial Activation

- (a) Localization assessment
- (b) Parental questionnaires - anchored to prior questionnaires
- (c) Speech perception assessed with the cochlear implant via direct input to processor
- (d) Mapping of the external speech processor

(10) Twenty-four Months Post-Initial Activation

- (a) Localization assessment
- (b) Hearing in noise assessment
- (c) Parental questionnaires - anchored to prior questionnaires
- (d) Speech perception with the cochlear implant via direct input to processor
- (e) Mapping of the external speech processor
- (f) Assessment of hearing in contralateral ear
- (g) Speech-language evaluation

d) Test Battery

The following test battery will be completed at various assessment intervals (preoperative, and at 3, 6, 9, 12, 18, and 24 months postoperatively) as defined in 6.iv. All assessment and mapping will be conducted at the Children's Cochlear Implant Center at UNC or at the Carolina Crossing research lab by board-certified audiologists.

i) Hearing Assessment

- (1) Air-conduction thresholds in both ears
 - (a) Air-conduction assessed with insert phones
 - (b) Assess bone-conduction thresholds if there is a PTA shift of >15 dB as compared to the previous interval
- (2) Aided thresholds with the external speech processor on will be measured using warble tones
 - (a) Frequencies assessed: 250-8000 Hz
 - (b) Masking presented to the contralateral ear (Turner, 2004).

ii) Tympanometry for each ear

iii) Speech Perception Measures in Quiet in ear of implant

- (1) Recorded materials will be presented at a comfortable listening level via direct input
- (2) Speech perception materials will be presented in a hierarchy, with advancement to the next test contingent on performance on the previous test

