
- (3) Test materials to include:
 - (a) 3 subtests of Early Speech Perception Test (ESP), if > 70% then,
 - (b) CNC words
- iv) Speech Perception in Noise in binaural condition (6, 12, and 24 months post-initial activation)
 - (1) Speech processor on
 - (a) Listening conditions, noise orientation
 - (i) Speech and noise at 0° azimuth.
 - (ii) Speech 0° azimuth and noise to implanted side
 - (iii) Speech 0° azimuth and noise to contralateral ear
 - (b) Speech perception materials
 - (i) BKB-SIN
 - (2) Speech processor off
 - (a) Listening conditions, noise orientation
 - (i) Speech and noise at 0° azimuth.
 - (ii) Speech 0° azimuth and noise to implanted side
 - (iii) Speech 0° azimuth and noise to contralateral ear
 - (b) Speech perception materials
 - (i) BKB-SIN
- v) Sound Field Localization Measures (3, 9, 18, and 24 months post-initial activation)
 - (1) Postoperative aided sound field assessment will be measured in the free field with the Sonnet speech processor turned on and with the processor turned off.
 - (2) Testing will be completed in a double-walled soundproof booth. Eleven loudspeakers are arrayed in a 180-degree arc, with speakers evenly spaced at 18-degree intervals. Speakers are mounted at ear level, all spaced approximately 1-meter from the listener.
 - (3) The stimulus is a 200-ms speech-shaped noise, presented at 70-dB SPL. The speaker used to present the stimulus is randomly selected from the 11 alternatives on each trial, with the caveat that each speaker is used 3 times during a block of 33 trials. At least one block of 33 trials will be obtained in each condition (with and without the processor turned on).
 - (4) The listener faces the middle speaker prior to and during stimulus presentation. The task is to identify the source of the noise. Feedback is provided during instruction and training trials, but not during data collection.
 - (5) Listening Conditions
 - (a) Cochlear implant speech processor off at the 3, 9, 18 and 24 month intervals
 - (b) Cochlear implant speech processor on at the 3, 9, 18 and 24 month intervals

- (6) Performance is analyzed by computing the normalized RMS error, a metric that characterizes a listener's ability to discriminate between sound source locations.
- (7) These procedures have been used successfully to test children as young as 4 years of age.

vi) Parent questionnaires

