- b) A single-subject design will be utilized, where each participant serves as his or her own control, for analysis of objective and subjective results. A single-subject design was chosen in order to accommodate the heterogeneity that is well known to characterize auditory prosthesis research. Repeated-measures ANOVA will be calculated with a p-value of ≤ 0.05 for statistical significance. Statistical analysis will be conducted with SPSS software.
 - i) Comparison of aided speech perception performance to the baseline condition (either unaided or aided with hearing aid, depending on the participants residual hearing) and in the post-initial activation intervals to evaluate trends over time
 - ii) Comparison of localization abilities to the baseline condition (either unaided or aided with hearing aid, depending on the participant's residual hearing) and in the post-initial activation intervals to evaluate trends over time
 - iii) Compute the overall rms error, random error, constant error, and adjusted constant error, as described by Grantham et al (2007)
 - iv) Comparison of subjective report scores in the post-initial activation intervals. Group means compared with Bonferroni's adjusted t tests or repeated-measure ANOVAs. Pearson's correlations will be used to analyze relationships between variables.
 - v) Subjective report scores will be compared to norms for this test. Group means compared with Bonferroni's adjusted t tests or repeated-measure ANOVAs. Pearson's correlations will be used to analyze relationships between variables.
- c) The incidence of interference between ears will be assessed at the 6,12 and 24 month post initial stimulation visit by comparing the speech perception performance in the 0° azimuth conditions for the contralateral ear only versus cochlear implant + contralateral ear conditions for each participant, as well as the individual's subjective report.

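### After activation CNC words are given only if ESP exceeds 70%, and section 8.b.i has no rule for a CNC not given; if such children are dropped, the group CNC gain tends to be overstated

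*Combined protocol and SAP*

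**What the plan says.** **Before surgery.** Eligibility (section 6.b.i, item 7) requires "Aided word recognition in the ear to be implanted of 30% or less as measured with CNC words (50-word list"). The candidacy list in 6.c has unaided and aided CNC, and the preoperative list has "Unaided word recognition with CNC words in both ears". None of these mentions ESP.

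**After activation.** Section 6.c.iv schedules speech perception by direct input to the processor at 3, 6, 9, 12, 18 and 24 months. Section 6.d.iii sets the order of tests: "Speech perception materials will be presented in a hierarchy, with advancement to the next test contingent on performance on the previous test". The steps are "3 subtests of Early Speech Perception Test (ESP), if > 70% then" CNC words. It adds: "Recorded materials will be presented at a comfortable listening level via direct input".

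**Lead-in to the battery.** Section 6.d opens: "The following test battery will be completed at various assessment intervals (preoperative, and at 3, 6, 9, 12, 18, and 24 months postoperatively"). It then refers to the visit list, where speech testing appears only after activation.

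**Analysis.** Section 8.b specifies repeated-measures ANOVA in SPSS at p ≤ 0.05. Section 8.b.i describes "Comparison of aided speech perception performance to the baseline condition" and comparison "in the post-initial activation intervals to evaluate trends over time". It names no test score. Neither 8.b.i nor the rest of section 8 says how a score that was not obtained is handled.

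**Status.** Speech perception with the implant on against the preoperative condition is part of the primary effectiveness endpoint (9.b). Each child's study endpoint is the 24-month visit (5.c).

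**The concern.** A CNC withheld by the gate is missing because the child did poorly in the ear under study. CNC is the only speech score that the written visit lists place both before and after implantation, so it is the natural score for the baseline comparison. A classical repeated-measures ANOVA keeps only children with every score in the model. Together these would tend to remove the children with the smallest gains. If all visits enter one model, a child who misses CNC only at 3 months also loses the 24-month score.

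At stake are the reported size of the group CNC gain and the number of children behind it. BKB-SIN, localization, the questionnaires and ESP itself are not gated.

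**Working it through.** **1. The plan's own figure.** 20 children with about 20% dropout leaves 20 × (1 − 0.20) = 16. The plan gives no effect size, SD, power, gate-failure rate or CNC distribution, so every input below other than 20, 16 and the 30% cap is an assumption.

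**2. Arithmetic of exclusion.** With k of n children not given CNC:

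overstatement = (k/n) × (mean gain of tested − mean gain of untested)

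Assume n = 16, preoperative score 5%, tested children reaching 50% (gain 45) and untested children at 5% (gain 0).

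| k | Overstatement | Gain, all children | Gain, tested only |
|---|---|---|---|
| 1 | 45/16 = 2.8 | 42.2 | 45 |
| 2 | 90/16 = 5.6 | 39.4 | 45 |
| 4 | 180/16 = 11.25 | 33.75 | 45 |

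A milder contrast (tested 40%, untested 20%) with k = 2 gives (2/16) × 20 = 2.5.

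**3. Six-visit simulation, 16 children, 20,000 replicates.** Assumed: mean CNC rising from 25% at 3 months to 50% at 24 months, SD 20, preoperative score about 5% and limited to 0–30, ESP–CNC correlation 0.6. The true 24-month gain is 44.3.

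| Failing at 3 / 24 months | Tested at 24 months | All six scores present | Children left of 16 |
|---|---|---|---|
| 10% / 2.1% | 44.9 (+0.6) | 48.2 (+3.9) | 12.3 |
| 25% / 7.7% | 46.1 (+1.8) | 53.0 (+8.7) | 7.7 |
| 40% / 15.8% | 47.5 (+3.2) | 57.5 (+13.2) | 4.3 |

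With correlation 0 and 25% failing, the gains are 44.3 and 44.4, so there is no bias. With preoperative score strongly tied to later ability (25% failing), the all-visit figure is 51.3, or +7.0. With no lasting child effect, both handlings give 46.2 against 44.4, or +1.8.

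**4. Wider simulation, 68 settings.** Assumed: the same CNC means, between-child SD 20, within-child SD 8, ESP–CNC correlation 0.5 or 0.8, 5% to 35% failing at 3 months and 0.3% to 16% at 24 months. The true gain is about 41. Large-sample bias in the 24-month gain:

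- baseline versus 24 months, complete pairs: +0.05 to +4.16 (+0.3 to +1.5 with 15% failing at 3 months); the standard error at n = 20 is about 4.7;
- all visits, complete cases: +1.0 to +12.4 (+2.6 to +6.4 with 15% failing); values above 10 need 35% failing;
- mixed model on change from the preoperative score: +0.01 to +3.48.

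The all-visit analysis kept 19.0 down to 7.8 of 20 children, or 15.2 down to 6.2 of 16. A separate simulation under similar assumptions gave about +1 to +11 for all-visit complete cases, with 47% to 96% of children kept, and about +0.0 to +3.2 for the mixed model on change.

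**5. Significance.** In 68 × 1,000 = 68,000 simulated trials of 20 children, significance of the 24-month gain never differed between full data, complete pairs and the mixed model on change. The all-visit complete-case test differed in 19 (19/68,000 = 0.03%).

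**6. Form of the model.** Nominal 95% intervals for the 24-month gain covered 90–97% with gate failures when the model was fitted to change. Coverage was 73–86% when baseline entered as a visit with a single random child effect.

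**The case against.** **The harm rests on steps the plan does not state.** The documents do not name CNC as the analysed score, do not say that incomplete cases are deleted, and do not say that all visits enter one model. This stands, and the point is conditional for that reason. The larger figures need all three.

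**The design is single-subject.** Children who do not advance remain visible in individual results. That is true, but section 8.b still specifies ANOVA, so a group result will be reported.

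**The effect at 24 months is small.** For baseline versus 24 months it stays below one standard error, and there the mixed model improves little on complete pairs (up to +3.48 against +4.16). This stands. The model's advantage is over an all-visit complete-case ANOVA, which the request in 8.b.i for trends over time makes a plausible reading.

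**The gate might also apply before surgery,** because the 6.d lead-in includes the preoperative interval. That the gate is post-activation only is an inference from the visit lists and the direct-input requirement; the Appendix A chart could not be read. Preoperative CNC is separately required either way.

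**A stronger reading.** A reader might infer that the gain is overstated whenever any child fails. It is only a tendency. A child who fails only at 3 months does not affect a baseline-versus-24-month comparison, and there is no bias if ESP is unrelated to CNC. In simulated 20-child trials with at least one exclusion, at correlation 0.5, the gain was not overstated in about 6–10% (24-month pairs) or 3–12% (all visits); at correlation 0.8, in about 0–2%.

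**Conclusion.** The point holds in conditional form. The gate, the ungated preoperative CNC and the absence of a rule in 8.b.i are in the documents. If CNC is the score and incomplete children are dropped, the group gain tends to be overstated. Rounded outward because all inputs are assumed, the size is about 0 to 5 points (usually under 2) for baseline versus 24 months alone. It is about 1 to 12 points, with a substantial loss of children, for one all-visit ANOVA with up to 35% failing at 3 months. It is zero if no child fails.

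A reader might go further and infer that the primary effectiveness result will be inflated or that the finding of benefit is in doubt. The documents support neither: the handling is unspecified rather than wrong, the other measures are not gated, and significance almost never changed in simulation. The change is worth making, at the low end of what should be changed.

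**What to change.** In section 8.b.i:

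1. Name CNC words in quiet, implanted ear, as the analysed score. Reconcile the preoperative wording in the 6.d lead-in with the eligibility, candidacy and preoperative lists.
2. For this score, replace the repeated-measures ANOVA with a linear mixed model (SPSS MIXED) on change from the preoperative score, with visit as a fixed effect and a random child effect, using every available post-activation visit.
3. Report at each visit how many children were not given CNC because of the gate.
4. Add a sensitivity analysis giving an ungiven CNC a floor value (0%, or the child's own preoperative score) or the lowest rank. Do not make this the sole primary rule or present it as a bound: in simulated 20-child trials, the interval from the zero-scored to the mixed-model gain held the true gain in only 0–55% of trials.

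**Cost.** Protocol wording and slightly more analysis work in the same software, with no added testing. The mixed model keeps a small upward bias. A child never given CNC contributes nothing to a change-score model, hence items 3 and 4. Under the assumptions of step 4, floor scoring understates the 24-month level (0%: −5.5 to 0.0 points; own score: −4.2 to 0.0). It can also distort the 3-to-24-month change (0%: 0.0 to +4.5; own score: −1.6 to +2.0), against +0.2 to +1.2 for complete cases.

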- (1) Speech, Spatial and Qualities of Hearing Scale (SSQ), (Gatehouse & Noble, 2004). The SSQ questionnaire assesses performance in three domains, hearing speech in quiet and noise environments (9 items), spatial or directional hearing (5 items) and sound qualities (8 items), which address sound segregation and listening effort. Each item is rated on a 10-point scale. Domain scores represent an average of item ratings. A modified version of this test will be used.
- (2) Bern SSD Questionnaire, (Kompis, Pfiffner, Krebs & Caversaccio , 2011). This is a 10-item questionnaire used for rating the subjectively perceived benefit of a hearing technology designed to be used for persons with UHL. A modified version of this test that can be completed by a parent will be used.
- (3) PedsQL Multidimensional fatigue scale (Varni, Limbers & Burwinkle, 2007). This is a validated scale for determining fatigue in young children, including general fatigue, sleep/rest fatigue and cognitive fatigue. Scores from this test have been previously demonstrated to be substantially affected by hearing loss in children (Hornsby et al 2013).

e) Aural Rehabilitation

- i) Participants and their parents will participate in aural rehabilitation sessions with a board-certified speech-language pathologist
- ii) Sessions will occur either in person or via tele-therapy at the time of the initial stimulation, 2-week follow up, 5 week follow up, and twice a month following for the first 6 months after the initial stimulation. Sessions will continue once per month for the next 6 months until the first annual follow up.
- (a) The option to continue on a once per month basis for the second year following the initial stimulation will be offered but will not be required.

7) Proposed Claims

- a) Demonstrate the effectiveness of cochlear implantation in children with moderate to profound UHL
 - i) Demonstrate an improvement in speech perception abilities, localization, and/or subjective benefit in an aided (cochlear implant on) versus an unaided (cochlear implant off) condition

- ii) Demonstrate improvement in ability, or improved ease, to participate in natural environments based on parental perception of benefit.

8) Statistical Analysis

- a) Descriptive summaries will be provided for the following: participant demographics, and frequency of major and minor complications/adverse events.

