A sample size of 20 participants was selected due to known variability in conventional cochlear implant recipient outcomes and to allow for possible dropouts (approximately 20%). A comparable study, Hansen, Gantz & Dunn (2013) evaluated 29 adult cochlear implant participants with UHL, which included etiologies of sudden sensorineural hearing loss, Meniere's disease, and vestibular schwannoma. Authors reported a high degree of variability in their sample. This project will not enroll all of the etiologies included in the Hansen, Gantz & Dunn (2013) analysis (such as, Meniere's Disease with intractable vertigo or history of vestibular schwannoma), therefore a smaller sample size was selected. The inclusion/exclusion criteria associated with this study, as compared to the heterogeneity of the Hansen, Gantz, & Dunn (2013) subject sample, will allow for more generalized comments about subjective and objective outcomes of cochlear implantation in pediatric cases of UHL.

If needed, statistical consultation will be sought from the North Carolina Translational and Clinical Sciences Institute (TraCS) or UNC Odum Institute.

9) Endpoints

- a) Safety endpoint
 - i) The primary safety endpoint is the evaluation of Adverse Events. All Adverse Events will be reported to the UNC IRB. If the UNC IRB or study investigators deem an Adverse Event unacceptable, then this would result in termination of the study.
- b) Primary effectiveness endpoint
 - i) The primary effectiveness endpoint is the comparison of speech perception, localization abilities and/or subjective report when the cochlear implant is on versus the preoperative unaided condition as well as changes in quality of life as measured by the Speech, Spatial and Qualities of Hearing Scale (SSQ), (Gatehouse & Noble 2004), the modified Bern SSD Questionnaire, (Kompis, Pfiffner, Krebs & Caversaccio , 2011) and the PedsQL Multidimensional fatigue scale (Varni, Limbers & Burwinkle, 2007).

10) Risk Analysis

- a) Potential risks to cochlear implantation

The following are risks associated with the MED-EL Synchrony implant, which is included in the device description:

1. Loss of residual hearing
2. Dizziness
3. Increased vertigo
4. Delay of healing of the scar
5. Impairment of the sense of taste

6. Potential for swallowing difficulties
7. Numbness
8. Increased tinnitus
9. Stimulation of the facial nerve
10. Temporary pain and uncomfortable sounds during stimulation

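### The effectiveness claim has no stated success rule across its three and/or domains, and its comparators differ between Sections 7, 8 and 9

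*Combined protocol and SAP*

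**What the plan says.** **The claim.** Section 7.a.i aims to "Demonstrate an improvement in speech perception abilities, localization, and/or subjective benefit", with the implant on versus off. Section 7.a.ii, under the same heading, adds "Demonstrate improvement in ability, or improved ease, to participate in natural environments based on parental perception of benefit".

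**The primary effectiveness endpoint.** Section 9.b.i is the "comparison of speech perception, localization abilities and/or subjective report when the cochlear implant is on versus the preoperative unaided condition", and continues "as well as changes in quality of life as measured by the Speech, Spatial and Qualities of Hearing Scale (SSQ", followed by the modified Bern questionnaire and the PedsQL fatigue scale. These are the same three parent questionnaires that Section 6.d.vi describes.

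**The tests.** Section 8.b: "Repeated-measures ANOVA will be calculated with a p-value of ≤ 0.05 for statistical significance". For speech, 8.b.i plans a "Comparison of aided speech perception performance to the baseline condition (either unaided or aided with hearing aid, depending on the participants residual hearing"; for localization, 8.b.ii plans a "Comparison of localization abilities to the baseline condition (either unaided or aided with hearing aid", again by residual hearing. Section 8.b.iii adds four localization scores: "Compute the overall rms error, random error, constant error, and adjusted constant error". Bonferroni is named only in 8.b.iv and 8.b.v, for subjective scores, in a phrase that offers t tests or repeated-measures ANOVA. Item iv compares post-activation visits and item v compares with norms.

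No section ranks the domains, says how many must succeed, or divides the significance level among them.

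**The concern.** Section 2 calls this a feasibility study, but gives demonstrating effectiveness as its primary purpose. A claim of that kind needs a rule fixed in advance. Here the same data could meet or miss the claim depending on three choices that the plan leaves open: how many domains must succeed, whether the parent-report and quality-of-life clauses are extra requirements, and which comparator applies. On the any-one-domain reading, the stated 0.05 is also not the error rate of the claim.

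**Working it through.** **Inputs.** Level 0.05 (8.b). Three domains (7.a.i, 9.b.i). Enrolment 20 (6.b.iii) with about 20% dropout (sample-size paragraph of Section 8), so 20 × 0.80 = 16 evaluable. Assumptions, since the plan is silent: two-sided tests, hence 0.05 / 2 = 0.025 in the favourable direction; one test per domain; no true effect in any domain; equal correlation between domains. The plan states no overall error rate and no power, so there is no figure of its own to reproduce.

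**1. Any one domain suffices.**
- Independent: 1 − (1 − 0.025)³ = 1 − 0.9269 = 0.073.
- Upper bound at any correlation: 3 × 0.025 = 0.075.
- Correlated domains (numerical integration of normal statistics; simulated paired t tests with n = 16):

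| Correlation | Normal | t tests, n = 16 |
|---|---|---|
| 0 | 7.3% | 7.3% |
| 0.5 | 6.3% | 6.3 to 6.4% |
| 0.75 | 5.2% | 5.3% |
| 0.9 | 4.2% | 4.3% |

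One test alone gives 2.5%. An F test over several visits has no direction. Counting a difference either way, the independent figure is 1 − 0.95³ = 14.3%, against 5%.

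**2. A separate parent-report test must also succeed.** The claim then requires that test to be positive, so the rate cannot exceed 0.025. Independent: 0.0731 × 0.025 = 0.2%. At correlation 0.5 it is 0.9%; at 0.75 it is 1.5%.

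**3. The quality-of-life clause is required, but any one questionnaire may meet it and also count as the subjective domain.** The rule reduces to any of three questionnaires. The rates are those of step 1 if unadjusted, and 2.5% or less with Bonferroni across the three.

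**4. Comparators.** Section 7.a.i uses implant on versus off. Sections 8.b.i–ii use a baseline that is aided or unaided by participant. Section 9.b.i uses preoperative unaided. Against the visible schedule in Sections 6.c and 6.d:

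| Measure | Listed preoperative result | Listed processor on and off |
|---|---|---|
| Localization | No | Yes (3, 9, 18, 24 months) |
| BKB-SIN | No | Yes (6, 12, 24 months) |
| CNC words | Yes | No |
| Questionnaires | Yes | No |

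No measure has both comparators in the visible text. Neither 8.b.iv nor 8.b.v names the preoperative comparison of subjective scores that 9.b.i calls for.

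**5. Cost of adjustment.** Paired t test, n = 16, standardized difference 0.75: noncentrality 0.75 × √16 = 3.0 on 15 degrees of freedom. Power is 80% at 0.05 and 62% at 0.05 / 3 = 0.0167. Holm, with a true effect in that domain only, gives about 63%.

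**The case against.** **Error rates.** A reader might infer that the plan carries a 5.3 to 7.3% false-claim rate as it stands. The documents do not support that. Items i and ii of 7.a stand under one claim with no *or* between them, and 9.b.i attaches quality of life by a phrase that can be read as a further requirement. If a separate parent-report test must also succeed, there is no inflation. The 5.3% figure rests on an assumed correlation of 0.75 and is not a floor. The rates also require no true effect anywhere. That is hard to credit for speech in the implanted ear: entry requires aided CNC of 30% or less, and Section 10.c cites an 80 to 85% chance of improvement at pure tone averages of 67 to 73 dB. Once one domain truly improves, the three-test figure no longer applies.

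**Comparators.** A reader might also infer that 9.b.i cannot be carried out for localization, or 7.a.i for speech. That goes too far. The opening of 6.d lists a preoperative interval for the battery, although it refers on to a list of postoperative visits. Section 8.b.ii presupposes a localization baseline, and the Appendix A figure is not shown. So localization is unclear rather than impossible. BKB-SIN supplies an on/off speech comparison for 7.a.i. Preoperative questionnaires are collected as an anchor, so for subjective scores what is missing is the comparison in 8.b.iv.

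**Design.** In a feasibility study of 20 children serving as their own controls, strict error control may reasonably be relaxed. That lowers the weight of the percentages. It does not supply the missing success rule or reconcile three different comparators.

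**Conclusion.** The point holds: the plan gives no success rule for its effectiveness claim, makes no adjustment across the three domains, and states three different comparators. This needs no numerical assumption.

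The size is conditional. If any one domain suffices, with one two-sided test each and no true effect in any, a false claim of improvement has a chance of 7.3% (independent), 6.3% (correlation 0.5) or 5.3% (correlation 0.75), and less at higher correlations. One test gives 2.5%. With a separate parent-report test also required, the chance does not exceed 2.5%. The correlations and the sidedness are assumptions, not figures from the plan. Whether the preoperative comparison in 9.b.i is available for localization cannot be settled from the visible text.

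**What to change.** In 7.a.i, 8.b and 9.b.i, state whether one domain is enough, and whether 7.a.ii and the quality-of-life clause must also be met. For each domain name one measure, one contrast and one visit that the schedule supplies. Twenty-four months is the only visit that lists speech in quiet, hearing in noise, localization and questionnaires together.

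- **Localization:** one named error score, processor on versus off.
- **Subjective report:** one named questionnaire score versus preoperative, with that comparison added to 8.b.iv.
- **Speech:** the sponsor's choice between BKB-SIN in one named noise condition, on versus off, and a speech-in-quiet score versus the preoperative score in the same ear, with the baseline stated as aided or unaided. CNC should not be treated as the required choice: 6.d.iii gives it only after more than 70% on the ESP, so some children may have no score.

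If any one domain may carry the claim, use Holm across the three at 0.05, or name a single primary measure. Report everything else as secondary, with estimates and confidence intervals.

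**Cost.** The changes are to wording, and the contrasts above use assessments already listed. With Holm, 16 evaluable children and a standardized difference of 0.75 in one domain only, power falls from 80% to about 63%. It is lower if fewer children have a score: with an assumed 12, power at 0.0167 is 45%. If all three domains have that difference, Holm power per domain is 71 to 74% (correlation 0.75 to 0). Naming a single primary measure avoids the adjustment.
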